After administering the consent quiz during the confirmation call, study staff will answer questions, review next steps, and clarify expectations. If a potential participant did not pass the consent quiz, study staff will be able to review the appropriate consent form sections and to re-administer the consent quiz. After completing the confirmation call, all eligible study participants will be considered enrolled into the study. Study staff will send via email secure Survey Gizmo links with the HIPAA authorization form, locator form and baseline survey. The HIPAA authorization form will now have an option for "I'm not sure." If someone selects the not sure option, they will be directed to call the study number to discuss their concerns or ask questions before moving forward in the enrollment process. Participants must agree to the HIPAA authorization to continue with the study. After agreeing to the HIPAA authorization, participants will click the next step link to complete the locator form. After completing the locator form, participants will click a link to complete the baseline survey. The brief locator form will request important contact information in order to locate participants for the follow-up survey and to re-engage with research and intervention activities, if needed. For participants who report they share their email address with someone else, we will ask them if they are sure it is okay for us to send information to this email address. If they say No or Prefer not to answer, they will be asked if they have a secondary email address they want to use. If someone does not complete the locator form or baseline survey, study staff will reach out to the participants to encourage them to complete these required activities. All participants will have one week to complete the enrollment process. Randomization will occur after completing the baseline survey. We will use block randomization to assign a group of three participants to each condition. We will wait till we have at least people randomized to Program A to begin the program. Participants will be informed of their assigned group after completing their baseline survey. WTV will notify participants of their randomly assigned program and the appropriate next steps for their specific program assignment. This change will allow us to conduct block random assignment computed by [name] and to allow us to equal number of people in each group throughout the study recruitment period. We will program Survey Gizmo to send the research team an automatic email when someone completes the baseline survey.

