
When Program A reaches approximately nine participants, we will form the next group assigned to Program A. We will follow-up participants who have incomplete digital data collection that occurs after consent for up to two times.

Figure A: Recruitment and Enrollment Flowchart

Recruitment activities will be conducted after IRB approval through March 31, 2020 or until we recruit up to 84 eligible CSOs, whichever comes first. We will track and document which recruitment strategies yield the best engagement. Please see examples of images and messaging we will use for different methods of recruitment. We plan to implement the following recruitment methods:

a. Recruitment channels

i. Participants will be recruited through the following methods as needed:

1. WTV Promotions (e.g., website callouts, emails, social media posts and 1:1 message) to existing and future WTV members.
2. Engagement of the membership group to suggest a friend and make a referral if they know anyone who fits the participant description.
3. Reaching out to existing partners who provide services to patients with OUD.
 - a. Sixth Street Community Center
 - b. Tempest
 - c. Rebel For A Change
 - d. Best Day Ever
 - e. Center for Motivation and Change

- f. JoinGroups.Com (medication-assisted treatment (MAT) for opioid addiction)
- 4. Develop recruitment strategies to increase diversification of study participants
 - a. Promote research study on the following professional counseling member websites:
 - i. Association of Black Psychologists (ABPsi)
 - ii. National Association of Black Social Workers (NABSW)
 - b. Develop new partnerships with providers who serve more diverse populations, including communities of color and lower SES
- 5. Targeted digital and local advertising efforts.
 - a. Facebook
 - b. Instagram
 - c. Google

3.3 Describe how prospective participants will be screened. Include information about: how, when, where, and by whom (by position or role, not by name). Describe any instruments that will be used or tests that will be performed during the screening process.

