Participant assigned to the CRAFT-A (Program A) and CRAFT-C (Program B) groups will have access to a 12-module on-line CRAFT intervention and asked to complete one module weekly for 12 weeks. Modules introduce CRAFT concepts and provide workbooks to assist participants in learning and applying the concepts. The modules include: 1) Introduction to CRAFT; 2) Communication Training; 3) Functional Analysis of Drug Using; 4) Positive Reinforcement; 5) Withdrawing Reinforcement; 6) Allowing Natural Consequences; 7) Problem-solving; 8) Life Enrichment; 9) Suggesting Treatment; 10) Recovery and Relapse; 11) Relationship; and 12) Recap of Skills. CRAFT-A participants also attend a weekly 60-minute online group sessions facilitated by a CRAFT-certified coach. CRAFT-C participants attend a weekly 60-minute individualized on-on-one coaching session with a CRAFT-certified coach. During weekly group or individual sessions concepts are briefly reviewed, questions are answered, and skills are practiced through role-plays of common situations. One-on-one sessions involve role-plays that are tailored to the participants' specific circumstances.

Counselors must complete their CRAFT training and certification prior to implementing Program A and Program B. In addition, CRAFT counselors must complete CITI training as limited personnel.

STUDY ACTIVITIES BY PROGRAM		
Experimental Programs		Standard Care Program
Program A & Program B		Program C
● Commit 1½ to 1¾ hours a week	● Commit 1 to 1½ hours a week	
● Watch a 12-module online support program delivered weekly	● Join a private online support forum for people with a loved one with an opioid use problem	
● Each module will be 30 to 45 minutes in length	● Gain access to knowledge and experiences of fellow CSOs shared in peer-led forum discussions	
● Attend weekly 60-minute online sessions facilitated by a CRAFT coach via Zoom or phone	● Post your own questions specific to your current situation and receive support from peers and WTV moderators	
● Review content from the weekly module	● Share your knowledge and experience to answer fellow CSOs' questions and to support others through their journey	
● Participate in a Question and Answer segment		
● Practice content with role-plays		
Program A		Program C
● Weekly sessions are in a small group with WTV coach and 3 to 8 study participants using Zoom	● Weekly sessions are one-to-one with WTV coach using Zoom	● Discussions are self-initiated and ongoing

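### Adverse-event collection opens at the first session, which PEER never has and which in CRAFT-A waits for a group; the survey clock also lacks a single start (minor)

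*Protocol*

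**What the plan says.** **Adverse events.** Protocol section 9.9 collects them from the first session of the intervention until the assessment 12 weeks after enrollment. Section 9.7 makes discomfort from research questions reportable when it leads the participant to stop.

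**Program formats (section 4.1).** Participants in both CRAFT arms are "asked to complete one module weekly for 12 weeks". CRAFT-C is one-to-one. For CRAFT-A, "Weekly sessions are in a small group with WTV coach and 3 to 8 study participants using Zoom". PEER is an online forum: "Discussions are self-initiated and ongoing".

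**Start of CRAFT-A (section 3.2).** On allocation: "We will use block randomization to assign a group of three participants to each condition". On starting: "We will wait till we have at least people randomized to Program A to begin the program". The number in that sentence is absent from the text at hand, and nothing here rests on the gap. On later groups: "When Program A reaches approximately nine participants, we will form the next group assigned to Program A".

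**Enrollment and surveys.** Section 4.2 places the follow-up surveys 8 and 12 weeks after enrollment. The primary hypothesis in section 1.2 speaks of three months after intake. In section 3.2, once the confirmation call is done, "all eligible study participants will be considered enrolled into the study". The same section then says "All participants will have one week to complete the enrollment process", and randomises after the baseline survey. Section 4.1 counts the locator form and baseline survey as part of enrollment. Section 6.2 makes agreement to the HIPAA authorization its last step.

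**The concern.** A collection window should open at an event that every participant in every arm has. Here it opens at one that PEER lacks and that CRAFT-A reaches only when others have been assigned. Followed literally, the rule gives a different start in each arm and none in PEER. It also leaves out the interval in which a CRAFT-A participant knows the assignment and is waiting to begin.

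The second issue is the survey clock. It starts at enrollment, which does not have one date, and it does not move with the start of the program. CRAFT-A can therefore have had slightly less of its 12-week course than CRAFT-C when treatment entry is assessed. The primary hypothesis predicts CRAFT-C above CRAFT-A above PEER. A lag in CRAFT-A would favour the first of these contrasts and work against the second.

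**Working it through.** The protocol states no waiting time, so there is no figure of its own to reproduce. The first two steps compare text; the third gives the scale under stated assumptions.

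**1. Adverse-event window by arm**

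| Arm | First session | Window opens |
|---|---|---|
| CRAFT-C | individual, needs no other participant | at that session |
| CRAFT-A | group, once enough people are assigned | after the wait |
| PEER | none | undefined |

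The baseline survey precedes randomisation, so discomfort caused by it lies before the window for everyone.

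**2. Date of enrollment.** Section 3.2 puts it at the confirmation call; sections 4.1 and 6.2 put it later. With one week allowed for the remaining steps, the readings differ by up to about a week, in every arm alike.

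**3. Course delivered by the primary survey**

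Inputs:
- Up to 84 participants (section 3.1); with equal arms, 84/3 = 28 in CRAFT-A.
- Length of recruitment is an assumption. Lower value: the six-month pilot of section 9.9 taken as 26 weeks, less 12 of follow-up, gives 14 weeks. Upper value: from the data and safety monitoring board's review on 15 November 2019 (section 9.10) to 31 March 2020 (section 3.2) is 137 days, and 137/7 = 19.6 weeks.
- Groups start at three, the lower limit in section 4.1. CRAFT-C starts at randomisation. Sessions are weekly. The lag from enrollment to randomisation is spread evenly over 0 to 1 week.

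Accrual to CRAFT-A: 28/14 = 2.0 and 28/19.6 = 1.43 per week.

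Mean wait when a group starts with its k-th member: ((k − 1)/2)/rate. For k = 3: 1/2.0 = 0.50 and 1/1.43 = 0.70 weeks. Simulation (2,000 replicates per setting; blocks of three or nine; uniform or even accrual) gives 0.41–0.49 and 0.57–0.69 weeks. It is slightly lower because the last incomplete group starts when recruitment closes.

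Session 12 falls at lag + wait + 11 weeks after enrollment.
- CRAFT-C: wait 0 and lag at most 1, so at most 12 weeks; all 12 sessions can be held by the survey.
- CRAFT-A: 11.3–11.6 sessions held on average. The shortfall is 12 − 11.6 = 0.4 to 12 − 11.3 = 0.7 of a session. Between 37% and 55% have at least one session after the survey.
- Survey at 13 weeks (a literal three months): 11.8–12.0 sessions held.
- Session 9, where treatment is suggested, falls at lag + wait + 8 weeks. Essentially everyone in CRAFT-A reaches it before week 12.

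Mean adverse-event window, with an average lag of half a week: CRAFT-C 12 − 0.5 = 11.5 weeks; CRAFT-A 12 − 0.5 − 0.41 = 11.1 to 12 − 0.5 − 0.69 = 10.8 weeks; PEER cannot be computed.

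**The case against.** Most of the case against a serious defect stands.

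- **Surveillance.** A reader might infer that PEER has no safety monitoring. It has: staff watch the forum (sections 4.1 and 9.9), the research assistant records events during contacts, and section 9.9 also says that all events during the study are documented. No comparison of adverse events between arms is among the aims or outcomes. Baseline-survey discomfort is not an arm-level problem, since whoever stops there is generally never randomised.
- **Size of the lag.** A reader might infer that CRAFT-A loses a substantial part of its course. If groups had to reach eight before starting, the same calculation gives a mean wait of 1.6–2.3 weeks and 9.7–10.4 sessions held. No section states such a rule. If a whole block is assigned at once, the wait specific to CRAFT-A can be zero.
- **Group rules.** About nine and three to eight look contradictory, but they can be read together: begin at three, fill to eight, and form the next group when a ninth person arrives. That still leaves open whether people join a course already running. If they do, they miss earlier group sessions, although nothing says that they lose the online modules.
- **CRAFT-C.** No section says that it starts without delay. Time spent on notification and scheduling would shrink the difference.
- **Delivery records.** Counselors already complete an activity checklist with ID numbers (section 8.2).

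None of this gives PEER a start to its window, or brings the CRAFT-A wait inside the one that section 9.9 defines.

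**Conclusion.** The adverse-event window holds as a defect on the text alone: undefined at its start in PEER, and open only after group formation in CRAFT-A. The enrollment date is ambiguous by up to about a week, without favouring any arm.

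The delivery difference is small: about 0.4 to 0.7 of a session by the 12-week survey if groups start at three, recruitment takes 14 to 19.6 weeks and CRAFT-C starts at once. It is less if three months means 13 weeks. A larger waiting lag needs groups that must fill before starting, which the protocol does not state. Nor does it support the inference that the CRAFT-C versus CRAFT-A comparison is invalid: waiting for a group is part of delivering a group program. Severity is minor.

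**What to change.** 1. In section 9.9, start adverse-event collection at randomisation in every arm. Also record baseline-survey discomfort that leads a participant to stop, as section 9.7 requires.
2. Count the 8- and 12-week surveys from randomisation in all arms, and do not shift them by arm or group. Give enrollment one date across sections 3.2, 4.1 and 6.2. For people already enrolled, check the consent wording first; adding the 8-week survey needed a consent addendum (section 6.2).
3. Reconcile sections 3.2 and 4.1 on group start, group size and late entry.
4. Record each participant's program start date, and use the existing activity checklists to report sessions delivered by the primary survey.

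The cost is protocol wording and the recording of start dates. The survey moves by at most about one week, equally in all arms. With groups starting at three, the randomisation clock returns only about 0.3–0.4 of a session to CRAFT-A; any remaining wait is described, not removed.

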4 STUDY PROCEDURES

4.1 Provide a detailed description of the study procedures in chronological order. As applicable, include information on: differences between the control and experimental groups, the number of follow-up visits, study visit windows, participant time commitment per activity, and the setting/location per activity.

Study procedures are outlined in the figure below. After screening eligible participants complete online enrollment, which includes providing informed consent, passing a consent quiz during the confirmation call by study staff (research assistant), agreeing to the HIPAA authorization form, and completion of the locator form and baseline survey. Participants are then randomized into one of three groups.

Participants assigned to the PEER group (Program C) will participate in an online peer support forum with other CSOs. Members of the forum post questions or comments to weekly peer-led discussions and receive responses and feedback from other CSO forum members. Members typically express concerns regarding their IP's wellbeing and ask other members to share any strategies they have employed when dealing with their IPs.

Interactions typically, are based either in 12-Step strategies members have learned (usually through Al-Anon or Nar-Anon Family Groups or Family Training Workshops provided by treatment programs) or in CRAFT skills learned (usually from treatment programs or other We The Village members). A staff member from We The Village monitors forum interactions to ensure members are interacting respectfully. This individual also will report any adverse or severe adverse events that members mention online.

Participant assigned to the CRAFT-A (Program A) and CRAFT-C (Program B) groups will have access to a 12-module on-line CRAFT intervention and asked to complete one module weekly for 12 weeks. Modules introduce CRAFT concepts and provide workbooks to assist participants in learning and applying the concepts. The modules include: 1) Introduction to CRAFT; 2) Communication Training; 3) Functional Analysis of Drug Using; 4) Positive Reinforcement; 5) Withdrawing Reinforcement; 6) Allowing Natural Consequences; 7) Problem-solving; 8) Life Enrichment; 9) Suggesting Treatment; 10) Recovery and Relapse; 11) Relationship; and 12) Recap of Skills. CRAFT-A participants also attend a weekly 60-minute online group sessions facilitated by a CRAFT-certified coach. CRAFT-C participants attend a weekly 60-minute individualized on-on-one coaching session with a CRAFT-certified coach. During weekly group or individual sessions concepts are briefly reviewed, questions are answered, and skills are practiced through role-plays of common situations. One-on-one sessions involve role-plays that are tailored to the participants' specific circumstances.

Counselors must complete their CRAFT training and certification prior to implementing Program A and Program B. In addition, CRAFT counselors must complete CITI training as limited personnel.

STUDY ACTIVITIES BY PROGRAM		
Experimental Programs		Standard Care Program
Program A & Program B		Program C
● Commit 1½ to 1¾ hours a week	● Commit 1 to 1½ hours a week	
● Watch a 12-module online support program delivered weekly	● Join a private online support forum for people with a loved one with an opioid use problem	
● Each module will be 30 to 45 minutes in length	● Gain access to knowledge and experiences of fellow CSOs shared in peer-led forum discussions	
● Attend weekly 60-minute online sessions facilitated by a CRAFT coach via Zoom or phone	● Post your own questions specific to your current situation and receive support from peers and WTV moderators	
● Review content from the weekly module	● Share your knowledge and experience to answer fellow CSOs' questions and to support others through their journey	
● Participate in a Question and Answer segment		
● Practice content with role-plays		
Program A		Program C
● Weekly sessions are in a small group with WTV coach and 3 to 8 study participants using Zoom	● Weekly sessions are one-to-one with WTV coach using Zoom	● Discussions are self-initiated and ongoing
● Weekly sessions follow a specific course outline and schedule	● Weekly sessions are tailored to the individual study participant	● Engagement can occur at any time of the day or night
		● Benefit from the extensive database of shared peer experiences

4.2 Briefly describe the sources or measures that will be used to collect data about participants. As applicable, include information on: instruments or surveys that will be administered, tests that will be performed, and the time points when each data will be accessed or obtained.

Data collected directly from participants:

Similar to screening and consent procedures, data collection for baseline, 8-week, and 12-week post enrollment follow-up surveys will be self-administered using Survey Gizmo software since participants may be located anywhere across the country. Participants will be directed to a separate link to complete the locator form and baseline survey after they complete the following steps:

1. Provide informed consent
2. Pass the consent quiz
3. Speak with a study staff person during the confirmation call
4. Agree to HIPAA authorization form

We will include a message that informs participants of the time estimate for completing the baseline survey, as well as the content of the baseline survey. They will be told that their contact information will be stored separately from the rest of the survey and never be directly connected to their survey answers. The baseline survey consists of socio-demographic questions, such as gender, age, race/ethnicity, and other standardized socio-demographic measures adapted from the GPRA instrument and the National Survey on Drug Use and Health. The questions in the 8-week and 12-week follow-up surveys will ask the same questions. The 8-week follow-up survey will enable the research team to assess changes in the lives of participants in an earlier phase of the intervention, with the 12-week assessing program impact at a later stage of the study.

	Behavior / Domain	Measure	Timepoints
1.	Socio-demographic questions	Measures adapted from GPRA and the National Survey on Drug Use and Health will include age, gender identity, race, ethnicity, sexual identity, and SES	Baseline only
2.	Treatment entry	Revised Supplemental Services Form	Baseline, 8-Week &12-Week Post Enrollment
3.	Relationship happiness	Relationship Happiness Scale	Baseline, 8-Week &12-Week Post Enrollment
4.	Missed work	SAS-SR – Work, Housekeeping, School sections (sections: A, B, C) only.	Baseline, 8-Week &12-Week Post Enrollment
5.	Depression, Anxiety, Anger	POMS	Baseline, 8-Week &12-Week Post Enrollment
	Physical illness	SF12 Health Survey	Baseline, 8-Week &12-Week Post Enrollment
6.	Learning CRAFT	Revised Family Training Survey	Baseline, 8-Week &12-Week Post Enrollment
7.	User satisfaction	Usefulness and Usability Survey	8-Week and 12-Week Post Enrollment only

Revised measures have been adapted specifically for CSOs with IPs with an OUP, as appropriate. In addition, we added questions specific to the impact of COVID-19 on the CSO, the CSO's contact with the IP, and IP's ability to access treatment and to receive quality treatment due to COVID-19 restrictions. The IP's treatment entry is the study's primary outcome and we need to understand the impact of COVID-19 on our participants' IPs gaining and receiving treatment to assess the study's impact on a primary outcome.

Participants may be contacted through email, text, calls, letters, and social media direct messaging. In addition, we will ask participants to give us the names and contact information for two people who can reach them if all other contact methods fail. Participants will be able to provide the messages we can send and/or leave, as well as any instructions they wish for us to follow when attempting to contact them or the contacts they shared with us.

Data collected from other sources (identify each source; e.g., health care provider, parent, public records):

N/A. We will only collect information directly from the study participants. We will not collect information from the CSO's IP.

4.3 Describe pre-defined criteria for removing participants from the study and the procedures for informing participants of their removal from the study. Include information on the handling of their data and measures to ensure individuals' safety and privacy after ceasing research activities.

Participants may be removed from the study for the following reasons:

- a. They engage in hostile behavior with other participants during online interactions
- b. They break the confidentiality and share personal information of other participants

Participants will be notified of their removal from the study by the Principal Investigator, [name]. The PI will call the participant to explain the reason for their removal. In addition, a formal letter will be sent to participants. Both the phone call and letter will explain the reason for their removal, how their data will be handled, and provide referrals for support, if needed.

Removed participants' data will be deleted and will not be used for analysis and dissemination. All contact information will be deleted within two weeks after informing the participant of their removal. We will track and document all reasons for removing participants in order to ensure they are not rescreened and re-enrolled into the study.

For protocols that meet the criteria for exempt research, skip to Section 7.

